3.3 Secondary Study Endpoints

Secondary cognitive endpoints will include the Minnesota Executive Functioning Scale (Carlson, 2014), and the NIH Toolbox Flanker Inhibitory Control and Attention Task (MacDonald, 2014). We will also evaluate potential behavioral and/or emotional changes with a caregiver-report paper and pencil measure (Child Behavior Checklist).

We will also evaluate feasibility and tolerability by collecting empty and full choline packages to monitor compliance. Serum choline levels will be obtained.

As part of the project, we will bring up to 40 participants (20 choline and 20 placebo) from our previous study (1R21AA019580 / 4R33AA019580) back to the University for a brief visit focused on examining the potential long-term cognitive effects of having taken choline or placebo. All who participated in the previous study will be eligible for the return visit. No study drug will be used at this visit and no blood will be collected. The measures administered will be cognitive outcome measures. The Elicited Imitation paradigm, used in the initial study, will be repeated using materials/items that have not previously been seen by the child. The Stanford Binet Intelligence Scales will be administered. The NIH Toolbox Picture Sequence Memory Test is a measure of episodic memory appropriate for ages 3 and up (McDonald 2014). The NIH Dimensional Card Sort Task is a measure of executive functioning from the same NIH Toolbox. The NIH Flanker Task is a measure of attentional control from the same NIH toolbox. The Narrative Memory subtest from the NEPSY-II is a measure of verbal memory for ages 3 to 16 (Korkman, Kirk et al. 2007). The Memory for Names subtest is another verbal memory subtest from the NEPSY-II. The child's height and weight will also be measured.

We will also bring up to 20 participants (10 choline and 10 placebo) from our previous study (1R21AA019580 / 4R33AA019580) back to the University for a neuroimaging visit focused on examining the potential long-term brain development effects of having taken choline or placebo. Participants will undergo MRI scans and brief neurocognitive testing at this follow-up visit.

3.4 Primary Safety Endpoints

No safety endpoints have been defined. Choline is a normal component of the human diet, so there are relatively few risks associated with supplementation. The doses to be used in the proposed project are below the upper tolerable limit for choline (1000 mg per day) and at or below the doses previously used in our pilot studies. At much higher doses than we are proposing, choline supplementation has been associated with mild hypotension. We observed no evidence of hypotension in 60 participants in the previous pilot studies. In the literature, some individuals report gastrointestinal disturbance associated with very high levels of choline supplementation. We observed no significant increase in GI symptoms with choline in 60 participants during the previous pilot studies. A full range of potential side effects will be screened.

Although allergic reactions to choline are not expected, we will monitor for a range of allergic symptoms nonetheless. There are no reported manifestations of intoxication of any kind nor overdose from the choline preparation to be used in this study. No toxic

CONFIDENTIAL

This material is the property of the University of Minnesota. Do not disclose or use except as authorized in writing by the study sponsor

effects have been reported.

NOTE that a Data and Safety Monitoring Board (DSMB) is in place and will review the study progress and adverse events.

4. Subject Selection and Withdrawal

4.1 Inclusion Criteria

1. Ages 2.5 years to 5 years of age*
2. Available parent or legal guardian capable of giving informed consent for participation. Participation of children under guardianship (wards of the state) needs to be authorized by a court order.
3. Modified Institute of Medicine (IOM) criteria for Fetal Alcohol Syndrome (FAS), Partial Fetal Alcohol Syndrome (PFAS), or Alcohol-Related Neurodevelopmental Disorder (ARND) (Hoyme, May, et al., 2005).

4.2 Exclusion Criteria

1. Known history of a neurological condition (ex. epilepsy, traumatic brain injury)
2. Known history of a medical condition known to affect brain function.
3. Known history of other neurodevelopmental disorder (ex. autism, Down syndrome)
4. Known history of very low birthweight (<1500 grams)

*For the follow-up studies of returning participants from the previous study (1R21AA019580 / 4R33AA019580), the inclusion/exclusion criteria will be the same as above except that the age range will be extended to incorporate the fact that the children are now older. The inclusion/exclusion criteria for the follow-up study will be from 2.5 to 15 years of age.

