4.3 Subject Recruitment and Screening

Participants will be recruited from two University of Minnesota Medical Center Clinics in which co-investigators see patients: The Fetal Alcohol Spectrum Disorders clinic ([name], Ph.D., [name], Ph.D) and the International Adoption Clinic (directed by [name], M.D.). Families of potential participants will be contacted by research staff. Visitors to these clinics may also see flyers and brochures describing the study at the time of their clinic appointment although they will not be recruited directly by their clinician. Mailings will also be sent to families of children with FASD via lists provided by the Minnesota Organization on Fetal Alcohol Syndrome (MOFAS). MOFAS has close working relationships with [name], [name], [name], [name] and both clinics. All recruitment materials will be submitted for IRB approval upon development, before use in the study. Telephone scripts will be utilized.

For the follow-up assessment, all participants from the previous study (1R21AA019580 / 4R33AA019580) will be invited to participate. Contact will be by letter and/or telephone call. Scripts will be utilized.

CONFIDENTIAL

This material is the property of the University of Minnesota. Do not disclose or use except as authorized in writing by the study sponsor

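### The 4.2 footnote re-applies the exclusion criteria to returning pilot children, contradicting 3.3 and 4.3; if followed, the long-term comparison selects on diagnoses made after randomisation

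*Combined protocol and SAP*

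**What the plan says.** Section 2 makes the long-term effect of choline a secondary objective, to be met by re-assessing children from the earlier randomised pilots. Three places say who may return.

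- Section 3.3, on the cognitive return visit: "All who participated in the previous study will be eligible for the return visit".
- Section 4.3: "all participants from the previous study (1R21AA019580 / 4R33AA019580) will be invited to participate".
- Section 4.2, footnote on returning participants: "the inclusion/exclusion criteria will be the same as above except that the age range will be extended". The range becomes 2.5 to 15 years. Nothing else is relaxed.

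The criteria carried over by the footnote are a known history of a neurological condition, a medical condition affecting brain function, another neurodevelopmental disorder, or birthweight under 1500 g.

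Section 3.3 also sets ceilings. For cognition, "we will bring up to 40 participants (20 choline and 20 placebo) from our previous study"; for imaging, "We will also bring up to 20 participants (10 choline and 10 placebo) from our previous study". No rule is given for choosing among families if more accept than there are places.

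Section 7.2 states an intention-to-treat approach. Section 7.3, on analysis populations, reads only as not applicable. Neither gives a separate rule for the follow-up.

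**The concern.** A comparison of pilot arms years later keeps the protection of randomisation only if membership does not depend on what happened after randomisation. The larger pilot took children aged 2.5 to 5 years (section 1.4), and the follow-up accepts them up to 15. In between, a child can have a first seizure, a head injury, or a first diagnosis of autism or another condition affecting the brain. Most of these bear on cognition and brain development, which is what the return visits measure.

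Staff who follow 3.3 and 4.3 would test such a child; staff who follow 4.2 would turn the child away. In the second case the child is never assessed, so no later analysis can readily restore the observation. If such diagnoses occurred at different rates in the two arms, the remaining groups would differ for reasons other than the treatment effect being estimated.

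**Working it through.** **1. Which criteria can depend on events after randomisation**

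| Criterion in 4.2 | Can first be recorded after pilot entry? |
|---|---|
| Neurological condition, such as epilepsy or brain injury | Yes |
| Medical condition affecting brain function | Yes |
| Other neurodevelopmental disorder | Yes for autism; Down syndrome is congenital |
| Very low birthweight | No, fixed at birth |

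Re-applying a criterion fixed before randomisation cannot select on a consequence of treatment. The problem is confined to the first three rows, and within them to conditions that arise or are first diagnosed later.

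**2. The population at stake**

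Section 1.4 gives 20 children in the R21 pilot and 40 more in the R33 pilot: 20 + 40 = 60. This reproduces the N=60 in section 7.1. If all 60 accepted, the ceilings would leave out 60 − 40 = 20 (33%) for cognition and 60 − 20 = 40 (67%) for imaging.

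**3. Bias from differential removal (illustration; all inputs assumed)**

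Let q be the share of an arm removed and k the gap, in SD, between kept and removed children. An arm's overall mean equals its kept mean minus qk, so the kept mean is too high by qk. The bias in choline minus placebo is

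bias = k × (q_choline − q_placebo).

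| Removed, choline / placebo | k = 0.5 | k = 1 | k = 1.5 |
|---|---|---|---|
| 10% / 10% | 0 | 0 | 0 |
| 5% / 15% | −0.05 | −0.10 | −0.15 |
| 5% / 25% | −0.10 | −0.20 | −0.30 |

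The sign reverses if more choline children are removed: 15% / 5% with k = 1 gives +0.10.

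**4. A second illustration, linking removal to the outcome**

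Assume outcomes N(0,1) on placebo and N(0.5,1) on choline. A child is excluded when a liability with correlation r to the outcome falls below the placebo 20th (or 30th) percentile, c. Treatment shifts the liability by 0.5r. With λ(x) = φ(x)/(1 − Φ(x)),

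observed difference = 0.5 + r × [λ(c − 0.5r) − λ(c)].

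| Placebo excluded | r | Choline excluded | Observed difference | Bias |
|---|---|---|---|---|
| 20% | 0 | 20% | 0.50 | 0 |
| 20% | 0.3 | 16% | 0.48 | −0.02 |
| 20% | 0.5 | 14% | 0.45 | −0.05 |
| 20% | 0.7 | 12% | 0.41 | −0.09 |
| 30% | 0.7 | 19% | 0.39 | −0.11 |

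For r = 0.5: c = −0.842, λ(c) = 0.350, λ(c − 0.25) = 0.255, so 0.5 + 0.5 × (0.255 − 0.350) = 0.45.

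**5. Comparison with sampling error**

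With outcome SD 1, the standard error is √(2/n): √(2/20) = 0.32 at 20 per arm and √(2/10) = 0.45 at 10 per arm. The biases in step 4 run up to 0.11/0.32, about a third of a standard error. The extreme corner of step 3 reaches 0.30/0.32, a little under one.

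**The case against.** The footnote's asterisk hangs on the age criterion, and its stated reason is that the children are now older. It may have been meant only to widen age, with no thought of re-screening. It does not say that exclusions are re-assessed at return or that later diagnoses count. If 3.3 governs in practice, nobody is turned away. This has force: the harm is conditional. But the footnote names the returning cohort and states that the other criteria stay the same, and no passage says which section prevails.

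A reader might infer that the long-term comparison is already no longer between randomised groups. The documents do not support that; it depends on staff following 4.2 over 3.3.

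A reader might also infer that a lasting benefit would be under-estimated. That needs choline to change the rate of excluding diagnoses, and nothing in the documents shows that it does. The pilot benefit in 1.4 is on a memory task. The illustrations assume the differential; with equal removal in the simple model, the bias is zero.

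Finally, a reader might take the ceilings by arm as a source of bias. Equal numbers per arm do not bias a contrast between arms, and a random draw within each arm preserves comparability. With voluntary return years later the ceilings may never bind. Consulting pilot allocation does not unblind the new trial. What remains is a missing selection rule.

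The conflict is also narrower than it may seem: the statement that all are eligible sits in the paragraph on the cognitive visit, and the imaging paragraph has no counterpart.

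**Conclusion.** The contradiction between the 4.2 footnote and sections 3.3 and 4.3 is plain in the text. If 4.2 is followed, the long-term comparison leaves out children on information that arose after pilot randomisation, contrary to the approach in 7.2.

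The size and direction of any bias cannot be determined, because the documents give no rate of new diagnoses, no split by arm and no correlation with outcome. Under the assumed inputs it is likely modest against the sampling error of so small a follow-up. The point concerns a secondary objective only. It is worth correcting because the correction is cheap and children who are not tested cannot be recovered later.

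**What to change.** Amend the 4.2 footnote to agree with 3.3 and 4.3. In substance: every child randomised in the R21 or R33 pilot is eligible for the return cognitive assessment up to the stated age limit, given consent; exclusion criteria are taken as at pilot entry and are not re-applied. Birthweight and congenital conditions are unaffected.

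Add to section 7 that diagnoses made since pilot entry are recorded as data, that the follow-up is analysed by randomised pilot arm, and, if wanted, that a sensitivity analysis omits children with such diagnoses.

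Apply the same principle to the imaging visit, apart from the imaging centre's own safety exclusions.

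The ceilings can stay. At most, state in 3.3 that if more families accept than there are places, children are chosen at random within pilot arm by someone not involved in testing. This leaves the 4.3 commitment to invite everyone intact.

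The cost is one amended footnote and a few added sentences, with no new visits. The small downside is that some children may be harder to test and outcome variance may rise slightly.

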4.3 Subject Recruitment and Screening

Participants will be recruited from two University of Minnesota Medical Center Clinics in which co-investigators see patients: The Fetal Alcohol Spectrum Disorders clinic ([name], Ph.D., [name], Ph.D) and the International Adoption Clinic (directed by [name], M.D.). Families of potential participants will be contacted by research staff. Visitors to these clinics may also see flyers and brochures describing the study at the time of their clinic appointment although they will not be recruited directly by their clinician. Mailings will also be sent to families of children with FASD via lists provided by the Minnesota Organization on Fetal Alcohol Syndrome (MOFAS). MOFAS has close working relationships with [name], [name], [name], [name] and both clinics. All recruitment materials will be submitted for IRB approval upon development, before use in the study. Telephone scripts will be utilized.

For the follow-up assessment, all participants from the previous study (1R21AA019580 / 4R33AA019580) will be invited to participate. Contact will be by letter and/or telephone call. Scripts will be utilized.

CONFIDENTIAL

This material is the property of the University of Minnesota. Do not disclose or use except as authorized in writing by the study sponsor

4.4 Early Withdrawal of Subjects

4.4.1 When and How to Withdraw Subjects

Participants may withdraw from the study at any time. The investigators may initiate the withdrawal of a study participant if significant side effects are apparent such as major gastrointestinal disturbance, diarrhea, hypotension, or allergic reaction.

4.4.2 Data Collection and Follow-up for Withdrawn Subjects

At the time of enrollment, contact information will be obtained for the participating family including address, home telephone number, cell phone number, and email address. We may also request contact information for a secondary caregiver of the child who would know their status in the future in case the study loses contact with the parent / primary caregiver. We will attempt to collect some follow-up information at 9 months for all withdrawn subjects (the normal point of study conclusion). If the withdrawn participant family is willing to be interviewed in person or by telephone about the child, we will collect side effect information, other health information such as the emergence of new medical problems, behavioral data (via the standard study behavioral rating instruments), and information about the reasons for study withdrawal.

5. Study Drug

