3.1 General Design

This is a randomized, double-blind, placebo-controlled study. Sixty children, male and female, between the ages of 2 years and 5 years at enrollment will be included.

Eligible participants will be randomized to treatment or placebo in a 1:1 allocation ratio. A block randomization procedure with variable block sizes will be used to maximize unpredictability of assignment.

Participants will receive the test article for nine months and will have an in-person baseline visit followed by 11 additional visits (9 telephone visits; 2 additional in-person visits) for a total of 12 visits. A telephone visit for purposes of safety and compliance will occur at 2 weeks. A telephone visit will be scheduled for 1 month after administration of the test article begins. Formal complete follow-up assessments will occur at 6 months and 9 months. Telephone visits for safety and compliance will occur at months 2, 3, 4, 5, 7, 8 and 10. Parent-report measures of behavior will be collected. Behavioral paradigms will be used to assess memory and other cognitive functions. Formal psychometric testing to establish developmental levels will be completed. Blood will be collected to assess compliance with the treatment and effect on blood choline levels. DNA will also be extracted for analysis of single nucleotide polymorphisms related to endogenous choline production. Plasma will also be analyzed for immune function and micro-RNA.

As part of the project, participants from the previous study (1R21AA019580 / 4R33AA019580) will be brought back to the University for a set of cognitive evaluations to assess the long-term effects of having taken choline/placebo previously.

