3.2 Primary Study Endpoints

The primary study endpoints will be cognitive assessments. These will include the Elicited Imitation memory task and the Stanford-Binet Intelligence Scales.

CONFIDENTIAL

This material is the property of the University of Minnesota. Do not disclose or use except as authorized in writing by the study sponsor

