6.1 Visits 1, 8, & 11 (Baseline and follow-up assessment visits)

Participants and their parent/guardians identified as described in Section 4.3 of this protocol will be asked to come for a baseline visit (Visit 1). This visit is expected to last for approximately 3 to 3.5 hours. Visits 8 and 11 will be similar, but slightly shorter (2.5 to 3 hours) because several tasks are not repeated. The following procedures will occur:

- Consenting process (Visit 1 only);
- Medical history (Visit 1 only) and physical exam
- Concomitant medications will be recorded
- Height
- Weight
- Head circumference
- Facial photograph to allow for detailed measurements (Visit 1 only)
- Blood pressure
- Blood collection for choline and metabolite (betaine, phosphatidylcholine, sphingomyelin, and trimethylamine-N-oxide (TMAO) level (3 ml tube).
- Plasma extracted from this whole blood will be analyzed for measures of immune function (cytokines) and micro-RNA..
- Extraction of DNA sample from any blood sample for single nucleotide polymorphisms related to endogenous choline synthesis (PEMT rs12325817)
- Astley & Clarren's FASD diagnostic evaluation including a photograph of the child's face for computer measurement and analysis (Visit 1 or Visit3)
- Stanford Binet Intelligence Scales, Fifth Edition (Visit 1 and 11 only)
- Elicited Imitation Paradigm, including video-recording to facilitate scoring afterward
- Minnesota EF Scale (MEFS), Early Childhood Version
- NIH Toolbox Flanker Inhibitory Control and Attention Task
- Beery Developmental Test of Visual-Motor Integration (VMI) (any visit)
- Scales of Independent Behavior (SIB) (any visit)
- Child behavioral questionnaires (CBCL); a parent-report instrument
- 24-hour Diet interview (for the parent/guardian to complete about the subject)
- Child Eating Behavior Questionnaire (CEBQ); a parent-report instrument
- Randomization (Visit 1 only)
- Training on how to store, mix, and administer the study medication (Visit 1 only)
- Adverse events will be recorded (Visits 8 & 11 only)
- Dispense a supply of the test article (30 packages at Visit 1)
- Provide instructions for returning for the next follow-up visit (Visits 1 & 8 only)

6.2 Visits 2, 3, 4, 5, 6, 7, 9, 10 & 12 (compliance/safety phonecontacts)

At each of these visits, study staff will place a phone call to the participant's parent/guardian. The following information will be collected:

CONFIDENTIAL

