7.1 Sample Size Determination

For purposes of sample size determination, the dependent measure was the percent of correct items on delayed recall of the EI task (averaged across two events per timepoint). The effect size from our completed trial was $d=0.66$. A power analysis was carried out using Optimal Design Software for Multi-level and Longitudinal Research (Version 3.01) to determine the sample size that would be necessary to detect a difference in linear change between treatment and placebo groups with this effect size (Feingold 2009). The analysis assumed that the data would be analyzed using a mixed models repeated measures design for a person-randomized trial, with an effect size $d=.66$, and a two-tailed type I error of 0.05. To achieve 80% power, a sample size of 58.5 participants (approximately 30 per treatment arm) is necessary. This is consistent with the significant group difference that was observed in the pilot trial. The sample size for the proposed study will therefore be fixed at 60 children. Combining participant data

CONFIDENTIAL

This material is the property of the University of Minnesota. Do not disclose or use except as authorized in writing by the study sponsor

for some outcome measures from the first set of pilot studies (N=60) and the proposed study (N=60) will provide additional power to further evaluate age, sex, and PEMT genotype as moderating variables.

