7.2 Statistical Methods

Statistical analyses will utilize an Intention to Treat (ITT) approach. Mixed models analyses with growth curve estimates will form the basis of the core analyses.

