7.3 Subject Population(s) for Analysis

Not applicable

8. Safety and Adverse Events

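### Children who withdraw are not scheduled for either primary cognitive test, so the intention-to-treat model must project their month-9 scores; inviting willing families to visits already planned is a cheap improvement

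*Combined protocol and SAP*

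**What the plan says.** - **Endpoints (3.2).** On the primary cognitive endpoints: "These will include the Elicited Imitation memory task and the Stanford-Binet Intelligence Scales".
- **Timing (3.1, 6.1).** "Formal complete follow-up assessments will occur at 6 months and 9 months", which are Visits 8 and 11. Elicited Imitation is given at baseline and at both; Stanford-Binet only at Visits 1 and 11.
- **Withdrawal (4.4.1).** Families may leave at any time, and "The investigators may initiate the withdrawal of a study participant if significant side effects are apparent". Section 4.4 describes no route by which a child stops study drug but stays in the assessments.
- **After withdrawal (4.4.2).** One contact is attempted at month 9. If the family is willing to be interviewed, in person or by telephone, "we will collect side effect information, other health information such as the emergence of new medical problems, behavioral data". The behavioural part is specified as rating instruments, so it cannot be read as the memory task. Reasons for leaving are also recorded.
- **Analysis (7.2, 7.3).** "Statistical analyses will utilize an Intention to Treat (ITT) approach", with mixed-model growth curves. Nothing is said about missing scores. Section 7.3, on analysis populations, reads "Not applicable".
- **Missing tests (note in 6.4).** Missing cognitive data are described as common and not a deviation. The note does not say how they are analysed.

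**The concern.** The analysis is meant to describe all randomised children, but the follow-up plan schedules the primary outcome only for those who remain. A likelihood-based mixed model uses every score that exists and handles the rest implicitly, as if a child who left would have followed the course of comparable children who stayed. If withdrawn choline children keep less benefit than that, the estimate for all randomised children is too high. No later analysis can restore a memory or IQ score that was never taken at age 3 or 4. Because withdrawal can follow side effects, leaving might be related to treatment.

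The concern is limited to children who leave the study. Nothing in the documents says that a child who only misses packets loses Visits 8 and 11.

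**Working it through.** **1. Scores available, by time of leaving (from the visit schedule)**

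| Child leaves | Elicited Imitation | Stanford-Binet |
|---|---|---|
| before month 6 | baseline only | baseline only |
| between months 6 and 9 | baseline, month 6 | baseline only |
| completes | baseline, months 6 and 9 | baseline, month 9 |

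**2. The plan's own figure.** Section 7.1 gives d = 0.66, two-tailed alpha 0.05, 80% power and N = 58.5, fixed at 60; there, "For purposes of sample size determination, the dependent measure was the percent of correct items on delayed recall of the EI task". The plain two-sample formula gives 4 × (1.960 + 0.842)² / 0.66² = 72.1 in total, not 58.5. The stated figure needs a variance factor of 58.5 / 72.1 = 0.81. Repeated measures could supply that, but the variance components are not given, so 58.5 can be neither confirmed nor called wrong. Here it serves only to scale the standard error (SE):

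- SE at N = 58.5: 0.66 / (1.960 + 0.842) = 0.2356 SD.
- SE at N = 60: 0.2356 × √(58.5/60) = 0.233 SD.
- With no gain from repeated measures the SE would be 2/√60 = 0.258 SD, making the ratios below slightly smaller.

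**3. Illustrative model for Elicited Imitation.** Assumptions, not taken from the documents: scores at months 0, 6 and 9; linear growth with group-by-time interaction; 30 per arm; compound symmetry with correlation 0.3, 0.5 or 0.7; benefit rising linearly to 0.66 SD at month 9 (0.66 × 6/9 = 0.44 at month 6). A share p = 10, 15 or 20% of the choline arm leaves (3, 4.5 or 6 of 30), and placebo leavers follow the placebo course.

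Where the scores already taken do not reveal the loss, overstatement = p × (benefit projected − benefit actually held at month 9):

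| Withdrawn choline children | Formula | 10% | 15% | 20% |
|---|---|---|---|---|
| leave at month 6, keep the 0.44 accrued | 0.22 × p | 0.022 | 0.033 | 0.044 |
| lose half | 0.33 × p | 0.033 | 0.050 | 0.066 |
| lose all (upper case) | 0.66 × p | 0.066 | 0.099 | 0.132 |
| lose all, already visible at month 6 | model fit | 0.039-0.046 | 0.057-0.068 | 0.075-0.088 |
| keep all, or no true effect | 0 | 0 | 0 | 0 |

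Generalised least squares fits agree with the formula rows at each correlation; the range in the model-fit row comes from the correlation. Non-zero cases run from 0.022/0.233 = 0.09 to 0.132/0.233 = 0.57 of one SE.

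**4. Placebo arm.** If placebo leavers truly score δ above the course projected for them, the effect is overstated by p × δ; if δ below, it is understated by the same amount. With δ = 0.33 and p = 10-20%, that is ±0.033 to ±0.066 SD.

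**5. Stanford-Binet.** No effect size is given, so no figure is claimed. With two time points the overstatement is p × the benefit lost. It differs from Elicited Imitation only for children leaving between months 6 and 9 whose loss already shows at month 6.

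**6. What the fix recovers, all-lost case.** If half the withdrawn families attend, the overstatement of 0.066-0.132 falls to 0.031-0.059 SD (leaving before month 6) or 0.037-0.072 SD (leaving after). At full attendance it is zero for early leavers. About 0.009-0.019 SD remains if benefit is lost only after month 6, because a straight line misfits a rise followed by a fall.

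**7. Power, all-lost case, 10% and 20% leaving both arms (normal approximation)**

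| Scores from leavers | Effect estimated | N with scores | Power |
|---|---|---|---|
| none | 0.66 | 54 / 48 | 77% / 72% |
| half attend | 0.625 / 0.587 | 57 / 54 | 75% / 67% |
| all attend | 0.594 / 0.528 | 60 | 72% / 62% |

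With no withdrawal it is 81%. Power falls because the effect in all randomised children is smaller.

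**The case against.** Section 4.4.2 says what will be attempted, not what is forbidden, and 6.1 does not make Visits 8 and 11 conditional on taking study drug. A reader might infer that withdrawn children are barred from testing, or that willing families are turned away; the text supports neither. It speaks of families willing to be interviewed about the child, not to bring the child for a session of 2.5-3 hours. **This stands:** the gap is that the tests are not scheduled, and it bites only for families who have left but would still accept testing, a number the documents do not give.

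Missing-at-random is the standard condition for the named model, and writing it down changes no estimate. The entry under 7.3 adds little once 7.2 has set the intention-to-treat principle. **This stands too:** the omitted statement is missing detail, and the substance is the uncollected scores.

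A reader might also infer that the trial will overstate choline's benefit. The documents do not establish that: they give no withdrawal rate or effect after withdrawal, and the placebo arm can move the estimate either way. The protocol's evidence points to the small end. Section 1.5 reports no arm difference in drop-out and no allergic reactions in the earlier studies, and 3.4 reports no hypotension and no significant increase in GI symptoms. Section 1.3 describes rodent benefit persisting after choline stopped. One qualification is that the earlier studies used a fixed dose, not the present weight-based one.

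None of this supplies the missing scores.

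**Conclusion.** The point holds as a cheap improvement, not as a serious flaw. The plan promises an all-randomised comparison but does not schedule the primary outcomes for children who withdraw, and those scores are lost for good.

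For Elicited Imitation the illustrated overstatement is 0.02-0.04 SD when accrued benefit is kept and 0.07-0.13 SD when all is lost. These figures rest on an assumed 10-20% choline withdrawal, the stated d = 0.66 and linear growth. The upper end, 0.57 of one SE, should not be read as the expected consequence; the likely size is well below one SE and the sign is not fixed.

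Two stronger readings should be set aside. The choline loss-of-benefit mechanism is proportional to the true effect, so it cannot by itself produce a false positive. Stanford-Binet is only modestly more exposed than Elicited Imitation, in the one circumstance shown in step 5.

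**What to change.** - **4.4:** distinguish stopping study drug from leaving follow-up.
- **4.4.2:** invite every randomised child whose family agrees to the cognitive tests already planned at Visits 8 and 11, whatever the study drug use. Keep the interview for families who decline.
- **7.2:** include these scores in the intention-to-treat model and state the missing-at-random assumption. Add one reference-based or delta-adjusted sensitivity analysis, applied to both arms, for scores still missing. This part needs no new data.

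No dose, withdrawal trigger or other clinical rule changes.

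**Cost.** Protocol and consent wording, re-contact effort, and staff time for visits already planned for every child. Payments are at most $75 + $100 = $175 per child, inside the planned maximum of 2 × $100 + $75 + 9 × $10 = $365. For 6-12 withdrawn children (10-20% of 60) that is at most $1,050-2,100. It is less if Visit 8 was already done, or if fewer procedures are attempted.

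**Downsides.** Recovery is partial, since some families will decline; half attendance removes roughly half of the overstatement. The estimated effect may be smaller, and power does not rise. What is gained is a less biased estimate for all randomised children.
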